3.7 Center pooling strategy

The study participants from MG0003 and MG0004 will be invited to participate in this study. The data from all sites will be pooled for analyses purposes.

3.8 Coding dictionaries

Adverse events (AEs) and medical histories will be coded using version 24.0 of the Medical Dictionary for Regulatory Activities (MedDRA®).

Medications will be coded according to B3 version Mar 2021 of the World Health Organization Drug Dictionary (WHODD).

3.9 Changes to protocol-defined analyses

In the protocol section 9.2.1, the intercurrent events to be considered are the use of rescue therapy prior to Day 43 and permanent treatment discontinuation (or withdrawal from study) due to TEAEs. In the SAP, we consider use of rescue therapy prior to Day 43 and permanent treatment discontinuation due to TEAEs as intercurrent events.

In the protocol, the treatment policy strategy is described for the analysis meaning that all data was planned to be analyzed regardless of study participants receiving treatment with rescue therapy. Summaries will also be presented for the efficacy endpoints where participants will be censored at the time that they take rescue medication. In the SAP, time to MG-ADL response will be analyzed censoring the data at the time of the use of rescue therapy and all other efficacy endpoints will be summarized following treatment policy.

Protocol amendment 3 did not mention how to treat IgG when participants receive rescue therapy. In the SAP, the IgG values up to and including 8 weeks after start date of rescue therapy will be excluded from the analysis.

In the protocol section 8.3.1, Hy's law is defined as $>3 \times \text{ULN}$ ALT or AST with coexisting $>2 \times \text{ULN}$ total bilirubin in the absence of $<2 \times \text{ULN}$ ALP, with no alternative explanation for the biochemical abnormality (ie, without waiting for any additional etiologic investigations to have been concluded). In this SAP, Hy's law is defined as (AST or ALT $\geq 3 \times \text{ULN}$) and TBL $\geq 2 \times \text{ULN}$ and ALP $< 2 \times \text{ULN}$ to be consistent with Rozanolixizumab program SAP.

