9. Study participant is treated with rescue therapy (IVIg, SCIG, PEX, or iv corticosteroids; see Section 6.5.4) during the Treatment Period. Those patients who received rescue therapy during the observation or no treatment with rozanolixizumab periods may continue in the study at the investigator's discretion and after discussion with Medical Monitor and/or UCB Study Physician. The following cycle of rozanolixizumab should in general not start earlier than 4 weeks following the last dose of IVIg, SCIG, or iv corticosteroids or the last PEX

session, unless there is a medical reason, and an earlier treatment initiation is being considered █ for the study participant as agreed upon with the Medical Monitor and/or UCB Study physician.

10. Study participant has a recurrence of aseptic meningitis (see also Appendix 14 [Section 10.14]).

Study participants **may** permanently discontinue rozanolixizumab **and** move into the Observation Period at the discretion of the Investigator, Medical Monitor, and Study Physician if any of the following events occur:

1. Study participant is noncompliant with the study procedures or medications in the opinion of the Investigator.
2. Study participant takes prohibited concomitant medications as defined in this protocol.

Investigators should contact the Medical Monitor, whenever possible, to discuss the withdrawal of a participant in advance. Investigators should attempt to obtain information on study participants in the event of withdrawal (eg, reason for withdrawal, any safety information).

In the event of study participant early withdrawal, the scenarios as described in Section 4.4 need to be considered.

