9.2.1 Intercurrent event handling rationale and impact on the study

In MG0007, every study participant, except those coming from MG0004, will start with an initial fixed mandatory cycle. Prior to dosing in the initial fixed treatment cycle, the study participant will be assessed for MG worsening (eg, an increase of 2.0 points on the MG-ADL or 3.0 points on the QMG scale). The study participant will be initially randomized to rozanolixizumab equivalent to approximately 7mg/kg or 10mg/kg weekly (QW). After the first treatment cycle, dose adjustments may be applied at the start of each treatment cycle based on Investigator's discretion. Dose adjustments may not be applied during a treatment cycle.

For the assessment of safety and tolerability, adverse events (AEs) recorded up to 8 weeks after the last sc infusion will be utilized for main analyses, regardless of study participants receiving treatment with rescue therapy.

For the analyses of efficacy endpoints, the intercurrent events to be considered are the use of rescue therapy prior to Day 43 and permanent treatment discontinuation (or withdrawal from study) due to TEAEs. Efficacy endpoints will be summarized in line with a treatment policy approach. With this approach, rozanolixizumab results will be analyzed regardless of study participants receiving treatment with rescue therapy. Summaries will also be presented for the efficacy endpoints where participants will be censored at the time that they take rescue medication.

Missing values will not be imputed.

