9.4 Planned efficacy and other analyses

9.4.1 Efficacy analyses

The main efficacy endpoint is the "Change from Baseline (Day 1) to Day 43 in MG-ADL score," for each of the first three 6-week treatment cycles where the Baseline of the respective cycle will be used as reference.

The summaries will be provided overall and by randomized treatment in-line with a treatment policy approach. Observed results will be presented for the different cycles (1 to n) regardless of the first cycle being mandatory or not. Missing values will not be imputed. Further summaries will be presented by the treatment received in each cycle.

The other secondary efficacy endpoints, Change from Baseline (Day 1) to Day 43 in QMG score, Change from Baseline (Day 1) to Day 43 in MG-C score, Change from Baseline (Day 1) to Day 43 in MG Symptoms PRO 'Muscle Weakness Fatigability' score, Change from Baseline (Day 1) to Day 43 in MG Symptoms PRO 'Physical Fatigue' score, and Change from Baseline (Day 1) to Day 43 in MG Symptoms PRO 'Bulbar symptoms' score, will be analyzed in the same way as the main secondary endpoint based on the MG-ADL.

Time to MG-ADL response (≥ 2.0 -point improvement from Baseline [Day 1]) for each treatment cycle will be summarized using time-to-event methodology (Kaplan Meier).

The time between consecutive treatment cycles will be summarized in order to provide information on how long the effect of rozanolixizumab lasts, ie, how long it will take to introduce a new cycle.

The number and percentage of participants achieving Minimal Symptom Expression (MG-ADL score of 0 or 1) at any time during the Treatment and Observation Periods will be summarized by cycle and by dose administration in that cycle.

Additionally, the number of treatment cycles will be summarized by treatment group.

Further summaries will be described in the SAP.

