3 DATA ANALYSIS CONSIDERATIONS

3.1 General presentation of summaries and analyses

For safety analyses, data will be summarized by dose levels of rozanolixizumab at the time of the event or measurement. For efficacy analyses, data will be summarized by the dose first received in the study. Additionally, efficacy data will be summarized by dose levels of rozanolixizumab received in each treatment cycle.

Statistical analysis and generation of tables, figures, participant data listings, and statistical outputs will be performed using SAS® Version 9.3 or higher. All tables and listings will use Courier New font size 9.

Descriptive statistics will be displayed to provide an overview of the study results. For continuous variables, descriptive statistics will include number of participants with available measurements (n), mean, standard deviation (SD), median, minimum, and maximum.

For categorical variables, the number and percentage of participants in each category will be presented. Unless otherwise noted, the denominator for percentages will be based on the number of participants included in the respective analysis set. Participants with missing data can generally be accounted for using the following approaches:

- For summaries of demographics and Baseline characteristics: summarize percentages based on all participants in the analysis set and include a “Missing” category (corresponding to participants with missing data for the variable being summarized) as the last row in the list of categories being summarized.
- For summaries of efficacy and safety endpoints, unless otherwise specified: summarize percentages based only on those participants with observed data for the variable being summarized. As the denominator may be different from the number of participants in the

analysis set being considered, the denominator should be displayed in the table. The general format for displaying this will be “n/Nsub (%).”

Unless otherwise noted, all percentages will be displayed to one decimal place. No percentage will be displayed for zero counts, and no decimal will be presented when the percentage is 100%.

For the purpose of the tabulations the lower and upper confidence limits for the percentages will be truncated at 0 and 100% respectively.

For PK concentration data, summary statistics will include geometric mean, geometric coefficient of variation (geoCV), 95% confidence interval (CI) for geometric mean, arithmetic mean, SD, median, minimum, and maximum.

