3.2.3 Mapping of assessments performed at Premature End of Treatment Visit

PEOT assessments will be assigned to the next scheduled site visit (following the last scheduled visit that the participant completed prior to PEOT) where each assessment is evaluated as per protocol. This approach means that there is a chance that PEOT data will be mapped to different visits according to the schedule of assessments.

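### The Day 43 efficacy results are labelled treatment policy, but after an early stop the planned data handling either leaves out the score (MG-ADL, QMG, MG-C) or labels an early one Day 43 (MG Symptoms PRO)

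*SAP*

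**What the plan says.** Protocol Section 9.2.1 states that "the intercurrent events to be considered are the use of rescue therapy prior to Day 43 and permanent treatment discontinuation" (or study withdrawal) due to TEAEs, and adopts a treatment-policy approach. SAP Section 3.9 narrows the list: "In the SAP, we consider use of rescue therapy prior to Day 43 and permanent treatment discontinuation due to TEAEs as intercurrent events". It then censors time to MG-ADL response at rescue and says of the rest that "all other efficacy endpoints will be summarized following treatment policy".

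Five further provisions decide what data exist at Day 43:

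- **Stopping.** The mandatory permanent-discontinuation list in Protocol Section 7.1.4 includes "Study participant is treated with rescue therapy (IVIg, SCIG, PEX, or iv corticosteroids; see Section 6.5.4) during the Treatment Period". Section 6.5.4 then requires the first 8 weeks of the Observation Period before the EOS visit.
- **End of the Treatment Period.** SAP Section 3.2.2 ends it after the Day 43 or the PEOT assessments. Protocol Tables 1-2 and 1-3 give both one column, and the next visit is Day 71.
- **Filing of PEOT scores.** "PEOT assessments will be assigned to the next scheduled site visit" at which the assessment is due (SAP Section 3.2.3). No other visit windowing applies (SAP Section 3.2.1).
- **Missing totals.** Protocol Section 9.4.1: "Missing values will not be imputed. Further summaries will be presented by the treatment received in each cycle".
- **Percentages.** SAP Section 3.1 says to "summarize percentages based only on those participants with observed data for the variable being summarized".

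SAP Section 4.7 plans no sensitivity analysis of efficacy.

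**The concern.** Treatment policy at Day 43 means using each participant's Day 43 score whether or not rescue or discontinuation came first. That needs a Day 43 score after the event. If the schedule collects none and the analysis neither imputes nor counts its absence, the label describes a property that the results lack.

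The endpoints at stake are the main efficacy endpoint (MG-ADL change to Day 43 in each of the first three cycles), the matching QMG and MG-C changes, the Day 43 responder percentages, and the three MG Symptoms PRO scales. These are descriptive, but Protocol Section 9.7 and SAP Section 4.4 foresee their use for submission. A reader told that they follow treatment policy will assume that participants who were rescued or stopped early are counted at Day 43.

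**Working it through.** There is no planned figure to reproduce: the study has no efficacy power calculation and states no within-cycle stop rate. The check has two parts.

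**1. Where a PEOT score is filed.** For each last completed visit I took the next visit marked as a site visit in Tables 1-2 and 1-3 at which the assessment is scheduled. Optional QMG visits were treated as scheduled.

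| Last visit completed | Initial cycle: MG-ADL, QMG, MG-C | Initial cycle: MG Symptoms PRO | Later cycles: MG-ADL, QMG, MG-C | Later cycles: MG Symptoms PRO |
|---|---|---|---|---|
| Day 1 | Day 8 | Day 15 | Day 15 | Day 43 |
| Day 3 | Day 8 | Day 15 | no visit | no visit |
| Day 8 | Day 15 | Day 15 | Day 15 | Day 43 |
| Day 15 | Day 22 | Day 43 | Day 29 | Day 43 |
| Day 22 | Day 36 | Day 43 | Day 29 | Day 43 |
| Day 29 | Day 36 | Day 43 | Day 43 | Day 43 |
| Day 36 | Day 43 | Day 43 | Day 43 | Day 43 |

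MG-ADL, QMG and MG-C reach Day 43 from 1 of 7 stopping positions in the initial cycle (Visit 7 completed) and from 2 of 6 in later cycles (Visit 5 or 6 completed). MG Symptoms PRO reaches it from 4 of 7 and from 6 of 6. So for the first three scales an early PEOT leaves the Day 43 cell empty. For MG Symptoms PRO in later cycles, a value from as early as the second week can be reported as Day 43.

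**2. What the empty cells can do.** All rates below are assumptions. The upper end, 15%, borrows the lead-in drop-out figure in Protocol Section 9.8, which is not a within-cycle rate.

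*Responder percentage.* Let p be the share of dosed participants without a Day 43 score. Responders as a share of all dosed = observed rate × (1 − p). With an assumed observed rate of 70%:

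- p = 5%: 0.70 × 0.95 = 66.5%
- p = 10%: 0.70 × 0.90 = 63.0%
- p = 15%: 0.70 × 0.85 = 59.5%

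The numerator is the same and the denominator is larger, so the observed-case rate cannot be the lower of the two. If a fraction r of the absent participants would have responded, the excess of the observed-case rate is p × (0.70 − r). For r from 0 to 40% it is 3.5 down to 1.5 percentage points at p = 5%, and 10.5 down to 4.5 at p = 15%.

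*Mean change.* If the absent participants' mean change is d points less favourable, the observed-case mean is shifted by p × d. For p = 3% to 15% and d = 1 to 4 MG-ADL points this is 0.03 × 1 = 0.03 to 0.15 × 4 = 0.60 points. The sign follows the sign of d, which the documents do not settle.

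**The case against.** The strongest reply is that the missing Day 43 visit is inferred. Protocol Section 7.1.4 does not say that rescue or a TEAE stop triggers PEOT. Its wording "permanently discontinue rozanolixizumab", with a move into the Observation Period, stands in the discretionary list, not the mandatory one. Section 4.4 can be read as requiring a participant still in a treatment cycle to complete it before EOS, and Sections 10.6 and 10.14 keep some stoppers in follow-up. Against this, Section 8.2.6 (active TB) does require a PEOT visit, Section 7.1.2 (QTc) moves the participant to the Observation Period, and SAP Section 3.2.2 lets PEOT end the Treatment Period. The documents do not settle the matter, and that itself needs correcting.

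A second reply is that the plan uses treatment policy to mean keeping observed data regardless of rescue, with non-imputation openly stated. That is fair as far as it goes: a participant rescued between the Day 36 dose and Day 43 can still attend Day 43, and that score is used. It does not supply a Day 43 value for someone who stopped in week two.

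Three stronger readings are tempting but unsupported:

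- **All Day 43 results describe cycle completers only.** Late PEOT values do count as Day 43 for MG-ADL, QMG and MG-C, and MG Symptoms PRO keeps early stoppers in later cycles.
- **Nothing else counts these failures.** By cycle, the SAP tabulates rescue use (11.2), TEAEs leading to permanent IMP withdrawal (8.2.2), infusions received (8.1) and Kaplan-Meier time to MG-ADL response (9.6). It also plans participant counts by visit (5.1) and displayed denominators (3.1). None of these is tied to the absent Day 43 scores.
- **The bias certainly favours rozanolixizumab.** Rescue is for participants with continuing symptoms, which makes this likely. But scores may improve after rescue, and a participant who stopped for a TEAE may have responded.

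**Conclusion.** The point stands in limited form. As the SAP is written, a participant whose early stop ends in a PEOT visit has no Day 43 MG-ADL, QMG or MG-C value and leaves those summaries. The same participant's MG Symptoms PRO score may be reported as Day 43 although it was taken weeks before. Neither is what SAP Section 3.9 promises. This rests on reading the shared Day 43/PEOT column and SAP Section 3.2.2 as replacing the Day 43 visit. If a calendar Day 43 visit is meant to be kept after stopping, the documents must say so.

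The size is unknown. That the observed-case responder rate is at least as high as the all-dosed rate is arithmetic. The 70% and the 5% to 15% range are illustrations only. For mean change the direction is likely but not certain. Time to MG-ADL response, minimal symptom expression and time between cycles do not depend on a Day 43 value and are outside the point. With no testing and no control arm, this is an error of description with a cheap remedy, and it should be corrected before the results are reported.

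**What to change.** 1. In SAP Sections 3.9, 9.1 to 9.5, 9.7 and 9.8, describe the Day 43 results as observed-case, including PEOT values filed to Day 43, and not as treatment policy. Reconcile Protocol Section 4.4, Tables 1-2 and 1-3, and SAP Sections 3.2.2 and 3.2.3 on whether a calendar Day 43 assessment is kept after dosing stops.
2. For each cycle, add a supplementary Day 43 responder percentage for MG-ADL, QMG and MG-C with all participants dosed in that cycle as denominator. Count as non-responders those without a true Day 43 score after rescue or permanent IMP discontinuation due to TEAEs. Label it a composite summary, because that is what it is. Show administrative and COVID-related exits as a separate category, not as treatment failures.
3. Beside it, give the number dosed, the number with a true Day 43 score, the number with a PEOT value filed to Day 43, and the reasons for absence.

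The analysis changes need no new data. The cost is SAP wording, some programming, and somewhat less favourable responder rates in the added row. The continuous endpoints are only relabelled; their sensitivity to the missing scores would have to be judged from the counts in item 3.

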4 STATISTICAL/ANALYTICAL ISSUES

4.1 Adjustments for covariates

Statistical testing is not planned for this study, hence adjustment for covariates will not be required.

4.2 Handling of dropouts or missing data

4.2.1 Efficacy data

The rules for handling missing data of individual items in the calculation of the QMG, MG-C, MG-ADL, MG Symptom PRO, and MG-QOL15r scores are described in [Section 13.1](#), [Section 13.2](#), [Section 13.3](#), [Section 13.4](#), and [Section 13.5](#), respectively.

For ordinal endpoints (eg EQ-5D-5L), the observed case method will be applied. No further imputation is used.

4.2.2 Dates and times

Partially or completely missing dates may be imputed for the following reasons:

- Classification of AEs as TEAEs;
- Classification of medications as past, prior, or concomitant medications;
- Durations of AEs.

Imputed dates will not be shown in listings. All dates will be displayed as reported in the database.

The following rules will be applied for partially or completely missing start dates:

- If year, month and day are all missing then assign the date of first dose of IMP. If an imputed start date is after the specified end date, then assign January 01 of the year of the end date, or the date of screening if this is later (if the latter imputation results in an end date that is earlier than the start date, then use January 01).
- If month and day are missing, and year is:
 - the same as the year of the first dose of IMP then assign the month-day of first dose of IMP. If the imputed start date is after the specified end date, then assign January 01, or the month-day of screening date if this is later (if the latter imputation results in an end date that is earlier than the start date, then assign January 01);
 - not the same as the year of the first dose of IMP then assign January 01.
- If only day is missing, and month-year is:
 - the same as the month-year of the first dose of IMP then assign the day of first dose of IMP. If the imputed start date is after the specified end date, then assign first day of the month, or the day of screening date if this is later (if the latter imputation results in an end date that is earlier than the start date, then assign first day of the month);
 - not the same as the month-year of the first dose of IMP then assign the first day of the month.

The following rules will be applied for partially or completely missing stop dates:

- If only the month and year are specified, then use the last day of the month. If an imputed stop date is after last contact date and last contact date is before the data cut-off date, then

assign last contact date as the stop date. If an imputed stop date is after last contact date and last contact date is after the data cutoff date, then assign data cutoff date as the stop date.

- If only the year is specified, then use December 31 of the known year. If an imputed stop date is after last contact date and last contact date is before the data cutoff date, then assign last contact date as the stop date. If an imputed stop date is after last contact date and last contact date is after the data cutoff date, then assign data cut-off date as the stop date.
- If the stop date is completely unknown, then use discharge date or data cut-off date. Discharge date refers to the date of the end of study visit for completed participants or the date of discontinuation for participants that were withdrawn. For any AEs with known start date after the date of discontinuation, the date of last contact will be used as the discharge date. For participants still ongoing in the study at the time of the data cut-off, and for whom no discharge date is available, the date of the data cut-off will be used instead of the discharge date.

Any medication with a start date on the first dosing date and time unknown, will be assumed to be concomitant.

Imputed AE dates will be used for the calculation of duration of AEs as described in [Table 4–1](#).

Table 4–1: Calculation rules for duration of AEs

Data availability	Onset date	Outcome date	Calculation rules
Complete data	D1	D2	$\text{Duration} = D2 - D1 + 1 \text{ d}$
Start date partially or completely missing	--	D2	$\text{Duration} \leq D2 - D0 + 1 \text{ d}$ Notes: D0 is imputed start date per above rules.
End date partially or completely missing	D1	--	For ongoing AE: $\text{Duration} \geq D3 - D1 \text{ d}$ For resolved AE: $\text{Duration} \leq D3 - D1 \text{ d}$ Notes: D3 is imputed end date per above rules.
Start and end date partially or completely missing	--	--	For ongoing AE: $\text{Duration} \geq D3 - D0 \text{ d}$ For resolved AE: $\text{Duration} \leq D3 - D0 \text{ d}$ Notes: D0 is imputed start date and D3 is imputed end date per above rules.

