8.2 Adverse events

8.2.1 Data considerations

Adverse events will be recorded from the time of informed consent until study completion. All AEs will be coded ([Section 3.8](#)).

In addition, AEs will be classified according to the Common Terminology Criteria for Adverse Events (CTCAE) Version 5 or later for severity. For any AEs where it is not possible to provide a CTCAE grading, the events will be assessed using a standard intensity classification (mild, moderate, and severe). For the purpose of reporting severe AEs, all CTCAE severity classifications will be mapped to a standard intensity classification as described below:

- Grade 1 - Mild
- Grade 2 - Moderate
- Grade 3, 4, 5 - Severe

These will be tabulated together with the AEs that were not classified according to CTCAE criteria (ie, all Grade 1 AEs as per CTCAE criteria will be included in the 'mild' category together with those AEs classified as mild as per the standard intensity classification). In the case a mapped standard intensity classification per above rule is different from the standard intensity classification on CRF, the worst case will be used as the standard intensity classification (ie, an AE with Grade 1 and moderate as intensity classification will be classified into moderate).

Any AE that occurred during the study will be defined as "**any AE**".

For each cycle, a **TEAE** is defined as any event that was not present prior to the first administration of rozanolixizumab of each treatment cycle or any unresolved event already present before the first administration of rozanolixizumab that worsens in intensity following exposure to treatment up to and including 8 weeks (56 days) after the last dose of each treatment cycle.

The following rules will be used to assign a TEAE to a study period in each study cycle:

- **Treatment Period:** a TEAE will be assigned to the Treatment Period for the tabulations if the start date of the event is on or after the date of the first administration of MG0007 IMP on Day 1, up to 7 days after the last dose of IMP in each cycle;
- **Observation Period:** a TEAE will be assigned to the Observation Period for the tabulations if the start date of the event is greater than the day after Treatment Period until 8 weeks (56 days) following the final dose in each study cycle.

An intermittent period AE is defined as AEs occurring after the 8-week (56-day) TEAE period, prior to the next cycle.

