A persistent AE is defined as an unresolved AE that extends continuously from MG0003 /MG0004 to MG0007 and does not worsen in intensity following exposure to IMP in MG0007. Persistent AEs will be recorded in MG0007 database.

Where dates are missing or partially missing, AEs will be assumed to be treatment-emergent unless evidence exists that does not allow the AE to be treatment-emergent. Handling of missing dates for classification of AEs as TEAEs is described in [Section 4.2.2](#).

A TEAE will be counted as a TEAE related to IMP if the response to the question “Relationship to Study Medication” is “Related”.

AEs will be presented as “number of participants (percentage of participants) [number of events]”. In this style of output, “[number of events]” will include all cases of an AE including repeat occurrences in individual participants, while “number of participants” will count each participant only once.

Persistent AEs, intermittent period AEs and other non-TEAEs will be listed only.

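### Partial AE start dates are imputed only against the study's first dose, although TEAEs are classified per cycle, so an AE can be placed in the wrong cycle, dose group or period

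*SAP*

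**What the plan says.** SAP 4.2.2 gives "Classification of AEs as TEAEs" as one purpose of date imputation. All its start-date rules turn on one anchor, the first dose of IMP:

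- Nothing known: "If year, month and day are all missing then assign the date of first dose of IMP".
- Only the day missing, in the first-dose month: if the month is "the same as the month-year of the first dose of IMP then assign the day of first dose of IMP".
- Only the day missing, in any other month: if the month is "not the same as the month-year of the first dose of IMP then assign the first day of the month".
- Only the year known: the first-dose date if it is the year of the first dose, otherwise 1 January.

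Fallbacks apply when an imputed start would fall after the recorded end. No rule mentions the first dose of a later cycle.

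SAP 8.2.1 works per cycle. A TEAE is "any event that was not present prior to the first administration of rozanolixizumab of each treatment cycle", or an existing event that worsens, "up to and including 8 weeks (56 days) after the last dose of each treatment cycle". What follows the window is separate: "An intermittent period AE is defined as AEs occurring after the 8-week (56-day) TEAE period, prior to the next cycle". Protocol 9.3.1 uses the same per-cycle window for the primary safety endpoint.

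For missing or partial dates, 8.2.1 adds that "AEs will be assumed to be treatment-emergent unless evidence exists that does not allow the AE to be treatment-emergent", and its next sentence refers the reader back to 4.2.2.

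SAP 3.6 groups whole-study AEs by the most recent dose level before onset. SAP 8.2.2 also tabulates TEAEs by cycle and for the Treatment Period alone.

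**The concern.** A rule with one anchor is serving a definition with as many anchors as there are cycles. It protects an AE in the month of the study's first dose by dating it to that dose. It gives no such protection in the month a second or later cycle begins, where the AE is dated to the 1st and so normally before the cycle.

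The imputed onset decides three things in the primary safety tables: whether the event is a TEAE, which cycle it belongs to and, through the most recent dose, which dose group. Doses may change at the start of any cycle, so a shift back across a cycle boundary can also cross a dose boundary. SAP 4.2.2 keeps imputed dates out of the listings, so a reader of the report could not see that this had happened.

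**Working it through.** The documents give no figure to reproduce, so this is date arithmetic on the stated rules.

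**Inputs**
- TEAE window: to 56 days after a cycle's last dose (SAP 8.2.1).
- Treatment Period for tabulating TEAEs: to 7 days after the last dose (SAP 8.2.1).
- Shortest usual gap between cycles: 4 weeks after the last dose (SAP 2.3.1). Longer gaps are expected: the gap categories in SAP 9.11 run to 1000 days.
- Assumption: six weekly doses, so last dose = Day 1 + 35 days.

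**Formula.** Let G be the days from the previous last dose to Day 1 of the next cycle, and d the calendar day of that Day 1. A day-missing AE that begins on or after Day 1 in the same month is imputed to the 1st, which is before the cycle whenever d > 1. The imputed date lies G − (d − 1) days after the previous last dose. Under 4.2.2 alone the AE stops being a TEAE only if G − (d − 1) > 56.

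**Worked example.** First dose 10 March 2021; cycle 1 last dose 14 April, so its window closes on 9 June. True onset is 3 days after cycle 2 Day 1, reported by month only.

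| G | Cycle 2 Day 1 | Imputed | Days after last dose | Class under 4.2.2 alone |
|---|---|---|---|---|
| 28 | 12 May | 1 May | 28 − 11 = 17 | TEAE, cycle 1 |
| 70 | 23 June | 1 June | 70 − 22 = 48 | TEAE, cycle 1 |
| 90 | 13 July | 1 July | 90 − 12 = 78 | Intermittent, not a TEAE |

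The true class is a cycle 2 TEAE in every row.

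**Grid.** Cycle 1 starts were spread over 730 consecutive days, with true onset uniform over the stated range and 4.2.2 applied alone.

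| True onset after cycle 2 Day 1 | Imputed before cycle 2 (any gap, 28–180 days) | Lost as TEAE: G 28–57 | G = 63 | G = 70 | G ≥ 87 |
|---|---|---|---|---|---|
| First 8 days | 85% | 0% | 20% | 43% | 85% |
| Whole window (0–91 days) | 16% | 0% | 6% | 11% | 16% |

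The percentages are shares of day-missing AEs, not of all AEs.

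**Treatment Period table.** The shift to the 1st is at most 30 days. If G > 37, the imputed date is more than 7 days after the previous last dose. A displaced AE then always leaves the Treatment Period table, even if it stays a TEAE.

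**Opposite error.** With the window closing on 9 June, a true intermittent onset on 20 June reported as June becomes 1 June, 48 days after the last dose, and counts as a TEAE. In the same grid, with no further cycle, 24% of day-missing AEs starting in the 61 days after the window closes are pulled back into it.

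**With the 8.2.1 presumption governing.** None of the displaced AEs is lost from the TEAE count, because a reported month that overlaps a cycle's window is not evidence against emergence. The presumption does not say which cycle or dose receives the AE.

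**The case against.** The strongest reply is that 8.2.1 already settles the matter: partially dated AEs are presumed treatment-emergent, 4.2.2 says only that dates may be imputed, and an imputed day is not evidence. This stands in part. A reader might infer from 4.2.2 that such AEs drop out of the primary TEAE count, but the documents do not establish that. If the presumption governs, none is lost. Even under 4.2.2 alone, none is lost when the imputed date is within 56 days of the previous last dose. The reply does not close the point, because 8.2.1 sends the handling back to 4.2.2 without stating precedence, and neither section assigns the cycle or dose.

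A reader might also infer a one-directional downward bias. The opposite error rules that out, and completely missing start dates normally go to the first dose and stay TEAEs.

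Nor is the misplaced share about 97%. The figure 29/30 is the share of cycles that do not start on the 1st of a 30-day month, not the share of AEs misplaced. Over the whole cycle 2 window that share is 16%.

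Three further points have some force. Protocol 8.3.8 has a study-level TEAE definition that would keep these AEs, but the primary analysis in Protocol 9.3.1 and SAP 8.2.1 is per cycle. Displaced AEs would not vanish: SAP 8.2.2 plans non-TEAE summaries, although 8.2.1 says non-TEAEs are only listed. And AEs are recorded at every scheduled visit, weekly during most of treatment, which should limit partial dates.

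**Conclusion.** The point holds as a mismatch between a stated rule and the definition it serves. As written, 4.2.2 dates a day-missing AE in a later cycle's start month to before that cycle, unless Day 1 is the 1st, and sends a year-only AE in a later year to 1 January. The firm consequence is that an AE can be placed in the wrong cycle and, where the dose changed between cycles, the wrong dose group. Loss of TEAE status is conditional: it needs 4.2.2 to override the 8.2.1 presumption and an imputed date more than 56 days after the previous last dose.

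The percentages rest on uniform onset and six weekly doses. The total effect on the primary tables cannot be stated, because the share of AEs with partial start dates is not given, and its net direction is not established. The change is worth making before the final analysis because it concerns classification for the primary safety endpoint.

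**What to change.** In SAP 4.2.2, for AE start dates:

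1. State that the 8.2.1 treatment-emergent presumption governs.
2. Test a partial date against every cycle. If the known month contains a cycle's first dose, impute that first-dose date unless the stop date rules it out.
3. If the known period contains several cycle starts, as a known year may, use a prespecified rule, for example the earliest cycle start compatible with the stop date.
4. Otherwise use the earliest date in the known period that lies inside a TEAE window.
5. Assign cycle and dose group from the resulting date.

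Reporting the number of AEs with a partial start date would let a reader judge the size of the effect.

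The cost is SAP wording and a small change to the imputation macro; no new data are needed. The downside is that some true pre-cycle intermittent AEs will be counted as TEAEs, which is the conservative direction 8.2.1 already takes. After short gaps, some late TEAEs of one cycle will also be credited to the next. No single-date rule avoids all misplacement, but this one is explicit and agrees with the stated presumption.
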